6.2 Subject Exclusion Criteria

Patients who meet any of the following criteria will be excluded from study entry.

General Exclusion Criteria:

Follicular lymphoma grade 3B

Concurrent aggressive non-Hodgkin lymphoma (eg, diffuse large B cell lymphoma [DLBCL])

Any anticancer therapy, including chemotherapy, hormonal therapy, investigational therapy, or radiotherapy, within 3 weeks, or 5 half lifes, whichever is shortest, prior to initiation of study treatment. However, the following are allowed:

- Hormone-replacement therapy or oral contraceptives
- Herbal therapy, provided it is discontinued at least 1 week prior to Cycle 1, Day 1
- Palliative radiotherapy for bone metastases, provided most recent fraction not given within 2 weeks of Cycle 1, Day 1 and most recent fraction was not administered to planned area of radiation while on study.

AEs from prior anticancer therapy that have not resolved to Grade \leq 1, with exception of alopecia or skin/nail hyperpigmentation.

Bisphosphonate therapy for symptomatic hypercalcemia within 2 weeks of cycle 1, day 1

- Use of bisphosphonate therapy for other reasons (e.g., bone metastasis or osteoporosis) is allowed. Denosumab should not be used while on therapy (see section 9.2.2)

Known clinically significant liver disease, including active viral, alcoholic, or other hepatitis; cirrhosis; fatty liver; and inherited liver disease

Active central nervous system (CNS) involvement of lymphoma.

- Patients with a history of CNS involvement of lymphoma are eligible, provided they received treatment greater than 30 days prior to cycle 1 day 1 and there is no evidence of involvement on most recent assessment.

Pregnant or breastfeeding, or intention of becoming pregnant during study treatment or within 5 month after the final dose of study treatment.

- Women of childbearing potential must have a negative serum pregnancy test result within 30 days prior to initiation of study treatment.

Known hypersensitivity to Chinese hamster ovary cell products, other recombinant human antibodies, or to any component of the atezolizumab formulation.

Inability to comply with study and follow-up procedures

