Treatment with systemic immunosuppressive medications (including but not limited to prednisone, cyclophosphamide, azathioprine, methotrexate, thalidomide, and anti-tumor necrosis factor [anti-TNF] agents) within 1 week prior to Cycle 1, Day 1

- Patients who have received acute, low-dose, systemic immunosuppressant medications (e.g., a one-time dose of dexamethasone for nausea or prednisone for intravenous contrast allergy) may be enrolled.
- Palliative systemic steroids for palliation of disease are allowed but must be discontinued at least 7 days prior to cycle 1, day 1
- The use of inhaled corticosteroids and mineralocorticoids (e.g., fludrocortisone) for patients with orthostatic hypotension or adrenocortical insufficiency is allowed.

History of severe allergic, anaphylactic, or other hypersensitivity reactions to chimeric or humanized antibodies or fusion proteins

Patients with prior allogeneic bone marrow transplantation or prior solid organ transplantation

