12.2.2 Assessment of Biomarkers Related to PD-L1, Tumor Biology, and Immune Cell Biology

Using immunohistochemistry, multiplex immunofluorescence, and fresh tissue immunophenotyping, we will assess biomarkers related to PD-L1 and/or immune cell biology and tumor biology that might contribute to our understanding of the mechanism of response to PD-L1 therapy and of the abscopal effect of radiation therapy in follicular lymphoma.

Immunohistochemistry of pre-treatment patient biopsies: Three to four (3-4) core biopsies will be fixed in formalin and allocated to the Molecular Cytology Core Facility for morphologic review and

immunohistochemistry (IHC). Immunohistochemical staining will be performed with antibodies against CD3, CD4, CD8, CD68, FoxP3, TBET, GATA3, B2M, MHC-I, MHC-II, PD-1, PD-L1, and PD-L2. We will follow previously well-established protocols for IHC analysis of FFPE tissue. (Appendix 9)

Flow cytometry analysis and sorting of pre and on-treatment patient biopsies Four (4) core biopsies will be placed in RPMI media and sent to Pathology. They will then be delivered to the Cell Marker Lab, where single cell suspensions will be generated. Clinical flow cytometry using 3-laser BD-FACSCANTO-10 instrument (Becton Dickinson Immunocytometry Systems (BDIS)) and 9-10 color assays (Appendix 9) will be performed with specific emphasis on markers likely to be affected by treatment with atezolizumab, including:

Basic T-cell subsets: CD3⁺ T cells and 2 subsets: CD3⁺CD4⁺ and CD3⁺CD8⁺.

Effector and memory subsets: defined by CD45RA, CD28, CD27, and CCR7

Regulatory T cells: defined by CD4, CD25, CD127, and CCR4.

Activation/exhaustion: defined by expression of PD-1, LAG-3, TIM-3, and CTLA-4

Preferred order of core biopsies to be obtained, media, and destination of sample:

| Core | Media | Destination |
|------|--------------|-------------|
| 1 | Formalin | Pathology |
| 2 | RPMI | Pathology |
| 3 | Formalin | Pathology |
| 4 | RPMI | Pathology |
| 5 | Formalin | Pathology |
| 6 | RPMI | Pathology |
| 7 | RPMI | Pathology |
| 8 | Flash Frozen | CSP |
| 9 | Flash Frozen | CSP |
| 10 | Formalin | Pathology |

Peripheral blood:

All patients will have four (4) additional tubes of blood drawn during screening and on treatment as per Appendix 1.

Two (2) Green Top tubes are to be drawn and sent to the HOTB lab for PBMC Storage.

One (1) Red Top Tube is to be drawn and sent to the HOTB lab for serum cytokines assay.

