12.2.3 Cytokine/ Chemokine Levels

To understand the prevalence of circulating cytokines/chemokines and the impact they may have on the clinical activity and/or safety of atezolizumab treatment, a panel of cytokines and chemokines may be investigated by ELISA or other protein assay methods. Levels of soluble PD-L1 in peripheral blood may also be assessed. One SST tube will be drawn during screening and on treatment as per Appendix 1, and will be sent to Zuckerman 1419 for processing and storage. (Appendix 9)

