14.6 Method of Analysis for Correlative Endpoints

Objective response rates, progression-free survival, and overall survival will be estimated for patients with preexisting tumor antigen restricted tumor infiltrating lymphocytes (TILs) and patients without preexisting tumor antigen restricted (TILs), and for patients who demonstrate a 2-fold expansion of T cell receptor (TCR) clonality and patients who do not demonstrate a 2-fold expansion of TCR clonality, and groups will be compared using Fisher's exact tests (ORR) and logrank tests (PFS and OS). Similar comparison will be performed to associate other biomarkers described in 2.3

with the outcomes. To assess the impact of treatment on peripheral blood cytokine/chemokine levels, Wilcoxon signed rank test will be used to test the intra-patient changes in these factors.

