20.1 Appendix 1**Flowsheet**

| | Screening | Cycle 1 | Low-dose radiotherapy | Cycle 2 | | Treatment Visits | Treatment Visits | Follow Up Visits | Off Treatment Visit |
|---|---|---------|-----------------------|--------------------|-----------|---|--|------------------------------|---------------------|
| | within 30 days of C1D1 unless otherwise specified | Day 1 | Cycle 1, Day 2 and 3 | Day 1 (+/- 2 days) | Day 14-20 | Cycle 3, 4, 6, 7, 8, 10, 11, 12, 14, 15, 16: Day 1 (+/- 2 days) | Cycle 5, 9, 13, 17: Day 1 (+/- 2 days) | Every 6 Months (+/- 14 days) | |
| Informed consent ^L | X | | | | | | | | |
| Medical history and demographics | X | | | | | | | | |
| Physical examination, including vital signs ^a , height, weight, and performance status | X | X | | X | | X | X | X | X |
| Adverse events | X | X | | X | | X | X | X | X |
| Concomitant medications | X | X | | X | | X | X | X | X |

| | | | | | | | | | |
|--|----------------|----------------|--|----------------|--|-----------------|----------------|----------------|----------------|
| Bone marrow biopsy & aspirate | X ^d | | | X ^d | | X ^d | X ^d | X ^d | X ^d |
| CBC w/ differential ^b | X | X ⁱ | | X ⁱ | | X ⁱ | X ⁱ | X | X |
| Chemistry panel ^c | X | X ⁱ | | X ⁱ | | X ⁱ | X ⁱ | X | X |
| TSH | X | X ⁱ | | X ⁱ | | X ⁱ | X ⁱ | X | X |
| Creatinine phosphokinase | X | X ⁱ | | X ⁱ | | X ⁱ | X ⁱ | X | X |
| PTT and PT/INR | X | | | | | | | | |
| Urinalysis | X | | | | | | | | |
| Infectious disease testing ^k | X | | | | | | | | |
| Pregnancy test (urine or blood) ⁿ | X ⁿ | | | | | | | | |
| Tumor Assessment | X ^e | | | | | X ^{em} | X ^e | X ^e | X ^e |
| Tumor biopsy | X ⁱ | | | X ⁱ | | | | | X ⁱ |
| Research blood samples | X ^g | | | X ^g | | X ^g | X ^g | X ^g | X ^g |

| | | | | | | | | | |
|-------------------------------------|---|--|----------------|--|--|--|--|--|---|
| Radiation oncology consultation | X | | | | | | | | |
| Low- dose radiotherapy ^h | | | X ^h | | | | | | |
| Electrocardiogram | X | | | | | | | | X |

^a Heart rate, systolic and diastolic blood pressure while the patient is in a seated position, and temperature.

^b Hemoglobin, hematocrit, platelet count, RBC count, WBC count, percent and absolute differential count (neutrophils, bands, eosinophils, lymphocytes, monocytes, basophils, other cells).

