^c Sodium, potassium, chloride, bicarbonate, glucose, BUN, creatinine, calcium, total and direct bilirubin, total protein, albumin, ALT, AST, alkaline phosphatase, amylase, lipase, LDH, uric acid, magnesium, phosphorus.

^d Bone marrow biopsy and aspirate is required within 60 days of C1D1, provided no treatment has been administered in the interim. For patients with involvement of follicular lymphoma at baseline, repeat testing is required only to confirm CR or as clinically indicated.

^e Imaging and reporting requirements for tumor assessment is described in Appendix 5. Patients will require a PET scan with diagnostic quality CT CAP (with intravenous and oral contrast, unless contraindicated) at study screening, Cycle 5, and EOT. A baseline PET with diagnostic CT CAP scan is required within 45 days of C1D1. For patients who have had a PET scan performed within 45 days of C1D1, a simulation scan (PET, CT, or MRI) will only be done if the patient is randomized to Arm 2 (RT arm). For patients who have not had a PET scan within 45 days of C1D1, baseline PET imaging will be a PET-simulation scan.

^f Tumor biopsy is required in all patients within 45 days of C1D1. Tumor FNA or core biopsy is required in all patients at Cycle 2 Days 14-20 (core biopsy is preferred). Tumor biopsy is recommended at time of progression on study. Tumor biopsy should be outside the field of radiation to allow for an accurate assessment of systemic changes to the tumor microenvironment following local irradiation. Acceptable samples include core needle biopsies for deep tumor tissue or lymph nodes or excisional, incisional, punch, or forceps biopsies for cutaneous, subcutaneous, or mucosal lesions

^g Research blood samples will be collected for correlative investigations as outlined in Section 12.2 of the protocol. Additional information about the workflow for correlatives can be found in Appendix 9.

^h Only if randomized to low- dose radiotherapy arm

ⁱ T3 and T4 should be tested only if TSH is abnormal.

- ^j Labs can be done within 5 days of day 1 of each cycle.
- ^k Infectious disease testing includes: Epstein-Barr virus (EBV) serology (EBNA IgG), Hepatitis B virus (HBV) serology (HBsAg, antibodies against HBsAg, hepatitis B core antigen), HCV serology (anti-HCV), and HIV 1 & 2 antibodies. HBV DNA test is required for patients who have positive serology for anti-HBc. HCV RNA test is required for patients who have positive serology for anti-HCV.
- ^l Within 45 Days of C1D1

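### The research-blood baseline is drawn at screening, before the washouts need be complete, so in exposed patients the cytokine change tested in Section 14.6 can mix drug withdrawal with the treatment effect

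*Combined protocol and SAP*

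**What the plan says.** Section 12.2.2 sets the research blood schedule: "All patients will have four (4) additional tubes of blood drawn during screening and on treatment as per Appendix 1". The tubes are two green (PBMC), one red (serum cytokines) and one purple, which is ordered for standard clinical flow cytometry with the remainder used for research. Section 12.2.3 adds a further serum tube: "One SST tube will be drawn during screening and on treatment as per Appendix 1".

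In the Appendix 1 flowsheet (Section 20.1), the screening column is headed "within 30 days of C1D1 unless otherwise specified". The row "Research blood samples" is marked at screening, Cycle 2, later treatment visits, follow-up and off treatment. Its C1D1 cell is empty. The row's footnote only points elsewhere: "Research blood samples will be collected for correlative investigations as outlined in Section 12.2 of the protocol". Neither Section 12.2 nor Appendix 9 gives a draw date.

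Section 6.2 bars anticancer therapy "within 3 weeks, or 5 half lifes, whichever is shortest, prior to initiation of study treatment". It bars systemic immunosuppressants in the last week before C1D1, and adds: "Palliative systemic steroids for palliation of disease are allowed but must be discontinued at least 7 days prior to cycle 1, day 1".

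For cytokines and chemokines, Section 14.6 plans one analysis: "Wilcoxon signed rank test will be used to test the intra-patient changes in these factors". It names no adjustment or sensitivity analysis for drugs in use at the baseline draw.

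**The concern.** The exploratory objective in Section 2.3 is to learn what atezolizumab, and the addition of radiotherapy, do to blood cytokine and chemokine levels. A paired test answers that only if the baseline reflects the patient's state just before treatment. Here the eligibility washouts protect the first infusion but not the baseline tube. A patient may be bled while taking prednisone or recent lymphoma therapy, then bled again after that drug has stopped and atezolizumab has started. The signed-rank test has no control for the difference.

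The protocol itself treats these drugs as immunologically active. Sections 9.2.1 and 9.2.2 warn that systemic corticosteroids and anti-TNF agents may blunt the immune benefit of atezolizumab, and Section 9.2.2 says immunosuppressants could change its activity.

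What is at stake is the interpretation of the biomarker results. A baseline tube cannot be redrawn once treatment has begun.

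**Working it through.** The plan gives no sample size, power or error rate for the blood analyses, so there is no stated figure to reproduce. The check has three parts.

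**1. Overlap of the screening window with permitted drugs.** Days at risk = 30-day window (Appendix 1) minus washout (Section 6.2).

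- Steroids and systemic immunosuppressants: 30 − 7 = 23 days (23/30 = 77% of the window).
- Anticancer therapy with the full 3-week washout: 30 − 21 = 9 days (9/30 = 30%). The shorter of the two limits applies, so 9 is a minimum; it grows when five half-lives take less than 21 days.
- Palliative bone radiotherapy: 30 − 14 = 16 days (16/30 = 53%).

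These are the days on which a draw could coincide with exposure. They are not the share of patients exposed.

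**2. Length of the interval compared.** Up to 30 untreated days precede C1D1. The on-treatment part depends on when the Cycle 2 tube is drawn, which is uncertain. In the flowsheet as extracted, the mark sits under Cycle 2 Day 1, but the tumor biopsy mark sits in the same position although its footnote places that biopsy on Days 14-20.

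- Cycle 2 Day 1: 21 days on treatment, 30 + 21 = 51 days in all.
- Cycle 2 Days 14-20: 21 + 13 = 34 to 21 + 19 = 40 days on treatment, 64 to 70 days in all.

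Section 14.6 does not say which later timepoint is compared with baseline.

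**3. Effect on the test, under assumed inputs.** The documents give neither the share exposed at the draw nor the shift on withdrawal. Assume a share f of 0 to 40% and a shift d of 0.5 or 1.0 SD of the within-patient change. Each change is simulated as N(0,1) + d × Bernoulli(f), with zero study-drug effect. The table gives the rejection rate of the two-sided 5% Wilcoxon signed-rank test over 4,000 runs per cell, with n = 25 (one arm) or n = 50 (arms pooled) and all pairs complete.

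| Share exposed | n=25, 0.5 SD | n=25, 1.0 SD | n=50, 0.5 SD | n=50, 1.0 SD |
|---|---|---|---|---|
| 0% | 0.045 | 0.049 | 0.046 | 0.046 |
| 10% | 0.058 | 0.069 | 0.064 | 0.090 |
| 20% | 0.070 | 0.133 | 0.101 | 0.230 |
| 30% | 0.101 | 0.242 | 0.174 | 0.436 |
| 40% | 0.154 | 0.375 | 0.259 | 0.682 |

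The simulation standard error is about √(0.05 × 0.95/4000) = 0.003 near 5% and at most √(0.25/4000) = 0.008. The test is two-sided, so the sign of the shift does not change the rates. The table covers drug withdrawal only, not untreated change.

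With a C1D1 pre-infusion baseline, the existing washouts would apply to the sample itself. That corresponds to the 0% row, apart from drug effects that outlast a washout.

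**The case against.** The strongest reply is that exposure at the draw is already recorded. Section 9.2.1 counts as concomitant therapy anything used from 14 days before the screening evaluation, and the flowsheet collects it at screening and later visits, so exposed patients can be identified. That stands, and it makes a sensitivity analysis feasible. But Section 14.6 does not plan one.

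Second, the size is unknown. The 23 and 9 days are bounds, the simulation inputs are assumed, and at 10% exposed with n = 25 the inflation is slight (0.058 to 0.069). This also stands.

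Third, the endpoints are exploratory, Section 12.2.3 says only that the panel may be investigated, and randomization balances prior drug use on average for any between-arm comparison. All true, but the one test named for cytokines is within-patient, where randomization gives no protection.

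Fourth, C1D1 is not a perfectly clean baseline. Section 6.2 allows acute low-dose immunosuppressants, and steroids may be given during treatment. A C1D1 draw reduces the problem without abolishing it.

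A reader might also infer more than the documents support:

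- That the bias mimics PD-L1 blockade. The documents do not establish what steroid withdrawal does to these markers.
- That the compared interval is 51 days with only 21 on treatment. That depends on the uncertain Cycle 2 draw day and on an unstated comparison timepoint.
- That the T-cell analyses are affected to the same degree. The signed-rank test is stated only for cytokines and chemokines. TCR clonality also uses biopsies, which have their own 45-day window and may be archival.

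**Conclusion.** The point holds as a limited design weakness. Baseline research blood may be drawn up to 30 days before C1D1, while every relevant washout counts back from C1D1 or treatment start. In patients exposed around the draw, the uncontrolled cytokine/chemokine change can mix drug withdrawal and untreated change with the study-treatment effect, in an unknown direction. Blood-based T-cell measures share the weakness; biopsy-based TCR measures are a separate matter.

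The plan permits this mixing but does not make it universal. The size turns on the share exposed, which the documents do not give. Under the assumed 0.5 to 1.0 SD shift, the false-positive rate of a nominal 5% test ranges from near nominal at 10% exposed (0.058 to 0.090 across both sample sizes) to 0.154-0.682 at 40%. The primary response analysis, PFS, OS and safety conclusions are unaffected. The change is worth making because it costs little and the sample cannot be recovered later.

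**What to change.** - In Appendix 1, draw the baseline serum tubes (red and SST) and PBMC tubes (green) at C1D1 before the first infusion, in both arms. This follows the washouts and precedes both atezolizumab and the radiotherapy on Days 2 and 3. State that the draw is same-day, because a flowsheet footnote allows labs within 5 days of Day 1.
- Leave the purple tube at screening if clinical flow cytometry is needed there. Research flow on its remainder then keeps the screening-baseline limitation and should be reported as such.
- State that later Day 1 research tubes are drawn before premedication and infusion; Section 5.1.2 allows premedication from Cycle 2.
- In Section 14.6, define the C1D1 value as baseline and name the timepoint or timepoints compared with it.
- Add a sensitivity analysis that uses the recorded concomitant medications to exclude patients exposed to steroids or immunosuppressants near a draw.

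The cost is a schedule edit and a few sentences in Section 14.6, with no extra visit and no extra tubes. The downside is that research tubes must be handled on the first infusion day. No change to the clinical washout rules is implied.

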12.2.3 Cytokine/ Chemokine Levels

To understand the prevalence of circulating cytokines/chemokines and the impact they may have on the clinical activity and/or safety of atezolizumab treatment, a panel of cytokines and chemokines may be investigated by ELISA or other protein assay methods. Levels of soluble PD-L1 in peripheral blood may also be assessed. One SST tube will be drawn during screening and on treatment as per Appendix 1, and will be sent to Zuckerman 1419 for processing and storage. (Appendix 9)

13.0 CRITERIA FOR REMOVAL FROM STUDY

13.1 Patient Discontinuation

Patients have the right to voluntarily withdraw from the study at any time for any reason. In addition, the investigator has the right to withdraw a patient from the study at any time. Reasons for withdrawal from the study may include, but are not limited to, the following:

Patient withdrawal of consent at any time

Any medical condition that the investigator determines may jeopardize the patient's safety if he or she continues in the study

Investigator determines it is in the best interest of the patient

Patient non-compliance

Every effort should be made to obtain information on patients who withdraw from the study. The primary reason for withdrawal from the study should be documented on the appropriate Case Report Form (CRF). However, patients will not be followed for any reason after consent has been withdrawn. Patients who withdraw from the study will not be replaced if they received any protocol treatment.

See Sections 10.3, 10.4, and 10.5 for assessments that are to be performed for patients who prematurely withdraw from the study during the treatment period.

13.2 Study Treatment Discontinuation

Patients must discontinue study treatment if they experience any of the following:

Pregnancy

Immune related adverse event that requires atezolizumab to be withheld for >42 days

Disease progression

In case of CT findings suggestive of pseudoprogression in patients with persistent clinical benefit investigator should contact the principal investigator to discuss further patient management. Because of the present potential for tumor flares immunotherapies, which result in early apparent radiographic progression (pseudoprogression/tumor immune infiltration), including the appearance of new lesions followed by delayed response (Wolchok et al. 2009), patients whose CT scans meet criteria for disease progression may continue to receive study treatment at the discretion of the principal investigator (1) if a moderate increase is seen in 1 lesion only or (2) if at least two the following criteria are met:

Absence of symptoms and signs, including worsening of laboratory values (e.g. increased LDH) that indicate unequivocal disease progression.

No declining ECOG performance status

Absence of tumor progression to critical anatomical sites (e.g. leptomeningeal disease) cannot be management protocol-allowed medical interventions

The primary reason for study treatment discontinuation should be documented on the appropriate CRF.

Patients with radiographic evidence of progression/ residual metabolically active disease who continue to receive study treatment will require the following:

- CT scan repeated 4-8 weeks later after documenting pseudoprogression
- If the CT scan shows persistent or further progression a tumor biopsy will be completed.

Patients who discontinue study treatment prematurely will not be replaced.

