9.3 Guidelines for Dosage Modification and Treatment Interruption or Discontinuation

ATEZOLIZUMAB treatment will be given as long as the patient continues to experience clinical benefit in the opinion of the investigator until the earlier of unacceptable toxicity, symptomatic deterioration attributed to disease progression, or any of the other reasons for treatment discontinuation listed in Section 13.1.

There will be no dose reduction for ATEZOLIZUMAB in this study. Patients may temporarily suspend study treatment for up to 42 days beyond the scheduled date of delayed infusion if study drug-related toxicity requiring dose suspension is experienced. If ATEZOLIZUMAB is held because

of AEs for >42 days beyond the scheduled date of infusion, the patient will be discontinued from ATEZOLIZUMAB and will be followed for safety and efficacy as specified in Section 10.2 and 10.3.

If a patient must be tapered off steroids used to treat AEs, ATEZOLIZUMAB may be held for additional time beyond 42 days from the scheduled dose until steroids are discontinued or reduced to a prednisone dose (or dose equivalent) of ≤ 10 mg/day. The acceptable length of interruption will be at the discretion of the investigator.

Dose interruptions for reasons other than toxicity, such as surgical procedures, may be allowed. The acceptable length of interruption will be at the discretion of the Principal Investigator.

Any toxicities associated or possibly associated with ATEZOLIZUMAB treatment should be managed according to standard medical practice. Additional tests, such as autoimmune serology or biopsies, may be used to determine a possible immunogenic etiology. Although most irAEs observed with immunomodulatory agents have been mild and self-limiting, such events should be recognized early and treated promptly to avoid potential major complications. Discontinuation of ATEZOLIZUMAB may not have an immediate therapeutic effect, and there is no available antidote for ATEZOLIZUMAB. In severe cases, immune-related toxicities may be acutely managed with topical corticosteroids, systemic corticosteroids, or other immunosuppressive agents.

Patients should be assessed clinically (including review of laboratory values) for toxicity prior to, during, and after each infusion. If unmanageable toxicity due to ATEZOLIZUMAB occurs at any time during the study, treatment with ATEZOLIZUMAB should be discontinued.

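### Section 13.2 permits atezolizumab after CT progression without requiring, on either route, that clinically unequivocal progression and unmanageable critical-site progression be absent

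*Combined protocol and SAP*

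**What the plan says.** Section 13.2 lists disease progression among the events after which study treatment must stop. It then makes an exception, which opens: "In case of CT findings suggestive of pseudoprogression in patients with persistent clinical benefit investigator should contact the principal investigator". Patients whose CT meets progression criteria may stay on treatment, if the principal investigator agrees, "1) if a moderate increase is seen in 1 lesion only or (2) if at least two the following criteria are met". The three criteria are:

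- A: no symptoms, signs or laboratory worsening that indicate unequivocal progression.
- B: no decline in ECOG performance status.
- C: "Absence of tumor progression to critical anatomical sites (e.g. leptomeningeal disease"; the line then runs into a garbled clause about protocol-allowed medical interventions. It most naturally limits the criterion to critical sites that such interventions cannot manage.

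Patients who continue have a repeat CT 4-8 weeks later. "If the CT scan shows persistent or further progression a tumor biopsy will be completed".

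Section 9.3 separately allows treatment "as long as the patient continues to experience clinical benefit in the opinion of the investigator" and ends it at the earlier of unacceptable toxicity, "symptomatic deterioration attributed to disease progression, or any of the other reasons for treatment discontinuation listed in Section 13.1". Section 13.1 states that "the investigator has the right to withdraw a patient from the study at any time" and gives among the possible reasons "Investigator determines it is in the best interest of the patient".

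**The concern.** The three criteria cover different hazards. A separates an ambiguous scan from progression that is clinically clear. C separates tolerable progression from dangerous progression. A count of two out of three lets one hazard be offset by the absence of the others, and the single-lesion route asks for none of them.

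The rationale in section 4.1.4 is that a scan may look worse because immune cells have infiltrated the tumor. That supports patience with an equivocal scan. It gives no reason to continue when the clinical picture indicates unequivocal progression, or when a critical site that cannot be managed has progressed.

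The stake is patient safety. Section 9.2.2 prohibits other anticancer treatment, including chemotherapy and radiotherapy, as concomitant therapy. Staying on atezolizumab therefore delays any alternative.

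**Working it through.** The plan gives no figure on this point and none is needed. The check is a reading of the rule, followed by a reading of the other sections that might close the gap.

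**The rule as logic.** Let A, B and C equal 1 when the criterion is met, and S equal 1 when there is a moderate increase in one lesion only.

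- Current rule: continuation is permitted if S = 1, or if A + B + C ≥ 2.
- With S = 0, 4 of the 8 combinations are permitted: one with all three criteria met and three with exactly one failing.
- With S = 1, all 8 are permitted, including the one in which all three criteria fail.
- Total: 4 + 8 = 12 of 16.
- Among those 12, A fails in 5, C fails in 5, and both fail in 2. At least one of A and C therefore fails in 5 + 5 − 2 = 8.
- If A = 1 and C = 1 are required on both routes, with B left open, 12 − 8 = 4 of 16 remain.

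These are counts of logical combinations, not probabilities. They ignore the clinical-benefit condition and section 9.3, which remove some of them in practice.

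**Two patients under route (2).**

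1. Progression at a critical site that cannot be managed, stable ECOG, and no symptoms, signs or laboratory change indicating unequivocal progression: A = 1, B = 1, C = 0. The sum is 2, so continuation is permitted.
2. Signs or laboratory values indicating unequivocal progression, no symptomatic deterioration, stable ECOG, no critical-site disease: A = 0, B = 1, C = 1. The sum is 2, so the list is satisfied.

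**Does another section require either patient to stop?**

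- Section 9.3 stops treatment for symptomatic deterioration. Neither patient has it.
- Section 9.3 also refers to section 13.1, but 13.1 gives a right to withdraw a patient on judgement, not a duty.
- Clinical benefit is a real condition, but section 9.3 leaves it to the investigator's opinion and gives no objective definition.
- Section 10.1 (Laboratory/Pathology Assessments) advises a biopsy at first radiographic progression but does not require it.
- The 4-8 week CT, and the biopsy if progression persists, come after the decision to continue. Section 13.2 attaches no explicit stop to their results.

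The written criteria are therefore the main objective check at the moment of decision.

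**Endpoints.** Section 14.5 takes best response only up to progression, and section 14.4 ends PFS at progression or death. Treatment after progression changes neither.

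**The case against.** The case for leaving the text alone has several parts.

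*The conditions at the start of the exception already exclude these patients.* It is reserved for scans suggestive of pseudoprogression with persistent benefit, and the principal investigator must agree. Someone with signs of unequivocal progression is hard to describe that way, and a careful principal investigator would probably stop. This stands as a limit on how often the gap would matter. It does not remove the gap, because section 13.2 then sets out a list that such a patient satisfies.

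*Leptomeningeal disease is a remote example.* Appendices 1 and 5 schedule PET with CT of the chest, abdomen and pelvis, then CT only. No brain or spine MRI and no CSF test is scheduled. Such disease would probably appear through symptoms and meet the section 9.3 stop, and section 6.2 excludes active CNS lymphoma at entry. This stands, so the point should not rest on that example. Criterion C covers critical sites generally.

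*Route (1) is narrower than it looks.* A moderate increase in one lesion most naturally means growth of an existing lesion, not spread to a new site. This stands too. It leaves growth of an existing lesion at a critical site, and it leaves clinical signs of unequivocal progression, with no criterion applied.

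*Exposure is bounded.* If a dose is given on the day of the decision and every 21 days after that, 2 doses precede a CT at 28 days (days 0 and 21) and 3 precede one at 56 days (days 0, 21 and 42). Examination, performance status and chemistry including LDH are scheduled at treatment visits. This limits the harm but sets no rule for stopping.

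*Requiring all three criteria would be too strict.* A reader might infer that ECOG decline should also be an absolute bar. The documents do not support that. Appendix 8 recognises tumor flare, continuing treatment through Grade 1-2 and resuming it once Grade 3-4 has improved. A transient ECOG decline may be part of a flare. This objection stands, and the fix respects it.

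**Conclusion.** The point holds as a modest gap in patient safety. Within the exception, section 13.2 allows any one criterion to fail under route (2) and requires none under route (1). No other section obliges a stop when a critical site that cannot be managed has progressed, or when signs or laboratory values indicate unequivocal progression, without symptomatic deterioration. The change is worth making because it is cheap and because section 4.1.4 offers no reason to continue in either situation.

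The size cannot be estimated. The documents give no expected rate of CT progression, pseudoprogression or critical-site progression. The outer limit is any of the 50 planned patients whose CT meets progression criteria.

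Two stronger readings should be resisted. A reader might infer that the protocol directs treatment to continue in such patients. It does not: continuation is discretionary and the patient or investigator may stop at any time. A reader might also infer that the efficacy results are compromised. Sections 14.4 and 14.5 rule that out for response and PFS.

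The conclusion assumes that the garbled third criterion refers to critical sites that allowed interventions cannot manage. If it means any critical-site progression, the gap is somewhat wider and the reasoning is the same.

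**What to change.** Amend section 13.2 so that, on both routes, treatment may continue after CT progression only if:

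- (a) no symptoms, signs or laboratory worsening indicate unequivocal progression; and
- (b) there is no progression at a critical anatomical site that protocol-allowed medical interventions cannot manage. This also repairs the garbled line.

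Leave ECOG decline to the principal investigator's judgement. This is no looser than the present text, which already tolerates an ECOG decline when the other two criteria are met. Keep the clinical-benefit condition, the principal investigator's discretion and the 4-8 week CT. Once (a) and (b) are mandatory, the two-of-three count is always met, so the two routes can be merged and the undefined word for the size of a single-lesion increase no longer decides eligibility. For clarity, a sentence can note that the stop in section 9.3 still applies.

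Whether atezolizumab must stop once the repeat CT and biopsy confirm progression is a separate, substantive choice and not part of this fix. Appendix 5 schedules CT every 3 months for patients treated beyond progression for as long as they stay on treatment, so the protocol contemplates longer continuation.

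The cost is a wording amendment, with no added patients, scans or biopsies. The downside is that an occasional true pseudoprogressor, whose laboratory change is read as unequivocal progression, may stop earlier.
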